6.10.5.2. Tipping Point Analysis

ASAS40, ASAS20, and mean change in ASDAS at Week 16 (Visit 8) will be analyzed based on the ITT Population using the tipping point method (Section 6.3.5).

6.10.5.3. Analysis Including Efficacy Data Post Treatment Discontinuation

Per recommendation in the 2010 National Research Council report *The Prevention and Treatment of Missing Data in Clinical Trials*, additional efficacy data for patients who prematurely discontinued Period 2 are collected during the Post-Treatment Follow-Up Period

(Period 4). Patients who discontinue treatment prior to Week 16 are instructed to schedule the Post-Treatment Follow-Up visit such that the post-treatment data will be collected 16-week after initial randomization. The efficacy data of ASAS40 at Week 16 will be summarized by treatment group, but no formal statistical comparison will be performed.

6.10.6. Health Outcomes/Quality-of-Life Analyses

The health outcomes and quality of life (QOL) measures are ASAS-HI, SF-36, Fatigue NRS, JSEQ, WPAI-SpA and Quick Inventory of Depressive Symptomatology–Self Report 16 items (QIDS-SR16).

The analyses of health outcomes and QOL measures for Period 2 will be based on the ITT Population. There will be no adjustment for multiple comparisons.

Descriptive statistics will be provided for Period 3 based on the Extended Treatment Period Population.

[Table RHBV.6.6](#) includes the description and derivation of the health outcomes and QOL measures.

[Table RHBV.6.7](#) provides the detailed analyses including analysis type, method and imputation, population, time point, and treatment group comparisons for health outcomes and QOL analyses.

Table RHBV.6.6. Description and Derivation of Health Outcomes and Quality-of-Life Measures

Measure	Description	Variable	Derivation / Comment	Imputation Approach if with Missing Components
ASAS Health Index	The ASAS-Health Index (ASAS-HI) is a disease specific health-index instrument designed to assess the impact of interventions for SpA, including axSpA. The 17 item instrument has scores ranging from 0 (good Health) to 17 (poor Health) (Kiltz et al. 2013). Each item consists of 1 question that the patient needs to respond to with either “I agree” (score 1) or “I do not agree (score 0).” A score of “1” is given where the item is affirmed, indicating adverse health.	ASAS-HI	All item scores are summed to give a total score or index. Range: 0 to 17 0 (good health) and 17 (poor health) Note, items # 7 and #8 may not be applicable for some patients. For those patients who ticked the response “not applicable”, the sum score is analyzed based on n=16 or n=15, respectively.	If ≥ 4 items ($>20\%$) have missing response, then ASAS-HI is missing. If <4 items ($\leq 20\%$) missing, then imputed sum = sum of scores from nonmissing items $\times n / (n - \text{no. of missing items})$, where n is the total number of applicable items, e.g. 15, 16, or 17. [ASAS Health Index User Manual (WWW)].
		ASAS-HI change from baseline – Major Secondary	Calculated as: observed ASAS-HI – baseline ASAS-HI	Missing if baseline or observed value is missing
Medical Outcomes Study 36-item Short-Form Health Survey	The SF-36 is a 36-item patient-administered measure designed to be a short, multipurpose assessment of health in the areas of physical functioning, role – physical, role – emotional, bodily pain, vitality, social functioning, mental health, and general health. The 2 overarching domains of mental well-being and physical well-being are captured by the Mental Component Summary and Physical Component Summary scores. The summary scores range from 0 to 100; higher scores indicate better levels of function and/or better health. Items are answered on Likert scales of	8 associated domain scores: 
 • Physical Functioning, • Role Physical, • Bodily Pain, • General Health, • Vitality, • Social Functioning, • Role Emotional, • Mental Health 2 component Scores: 
 • MCS Score • PCS Score 	Per copyright owner, the QualityMetric Health Outcomes™ Scoring Software 4.5 will be used to derive SF-36 domain and component scores. After data quality-controls, the SF-36 software will re-calibrate the item-level responses for calculation of the domain and component scores. These raw scores will be transformed into the domain scores (t-scores) using the 1-week recall period. The procedure to derive the SF-36 scores is described in Appendix 6 . It entails exporting the patient data in a CSV or tab-delimited file for import, generation of the SF-36 scores and reports, and export of the	Missing data handling offered by SF-36 software will not be used.

Measure	Description	Variable	Derivation / Comment	Imputation Approach if with Missing Components
	varying lengths. The SF-36 version 2 (acute version) will be used, which utilizes a 1-week recall period (Ware [2000]).		calculated scores in a CSV or tab-delimited file for integration into SDTM/ADaM datasets. The summary scores range from 0 to 100.	
		PCS change from baseline – Major Secondary	Calculated as: observed score – baseline score	Missing if baseline or observed value is missing
		MCS and domain scores change from baseline	Calculated as: observed score – baseline score	Missing if baseline or observed value is missing
Fatigue Severity Numeric Rating Scale	The fatigue severity NRS is a patient-administered single-item 11-point horizontal scale anchored at 0 and 10, with 0 representing “no fatigue” and 10 representing “as bad as you can imagine” (Naegeli et al. 2013). Patients rate their fatigue (feeling tired or worn out) by circling the 1 number that describes their worst level of fatigue during the previous 24 hours.	Fatigue Severity NRS	Range: 0 to 10. 0 (no fatigue) and 10 (as bad as you can imagine).	Single item, missing if missing
		Fatigue Severity change from baseline	Calculated as: observed Fatigue Severity NRS – baseline Fatigue Severity NRS	Missing if baseline or observed value is missing
Work Productivity and Activity Impairment Questionnaire—Spondyloarthritis	The Work Productivity Activity Impairment—Spondyloarthritis (WPAI-SpA) consists of 6 questions to determine employment status, hours missed from work because of spondyloarthritis, hours missed from work for other reasons, hours actually worked, the degree to which spondyloarthritis affected work productivity while at work, and the degree to which spondyloarthritis affected activities outside of work. The WPAI-SpA has been validated in	percentage of absenteeism	% work time missed due to problem: $(Q2/(Q2 + Q4))*100$	if Q2 or Q4 is missing, then missing
		percentage of absenteeism - change from baseline	Calculated as: observed value – baseline value	if baseline or observed value is missing, then missing
		percentage of presenteeism	% impairment while working due to problem: $(Q5/10)*100$	if Q5 is missing, then missing
		percentage of presenteeism - change from baseline	Calculated as: observed value – baseline value	if baseline or observed value is missing, then missing
		overall work impairment score	% overall work impairment due to problem: $(Q2/(Q2+ Q4) + [(1-Q2/(Q2+Q4))*(Q5/10)])*100$	if any of Q2, Q4, or Q5 is missing, then missing

Measure	Description	Variable	Derivation / Comment	Imputation Approach if with Missing Components
	the rad-axSpA patient population (Reilly et al. 2010). Four scores are derived: percentage of absenteeism, percentage of presenteeism (reduced productivity while at work), an overall work impairment score that combines absenteeism and presenteeism, and percentage of impairment in activities performed outside of work. Greater scores indicate greater impairment.	overall work impairment score - change from baseline	Calculated as: observed value – baseline value	if baseline or observed value is missing, then missing
		percentage of impairment	% activity impairment due to problem: $(Q6/10)*100$	if Q6 is missing, then missing
		percentage of impairment - change form baseline	Change from baseline is calculated as: observed value – baseline value	if baseline or observed value is missing, then missing
Jenkins Sleep Questionnaire	The Jenkins Sleep Evaluation Questionnaire (JSEQ) is a 4 item scale designed to estimate sleep problems in clinical research. The JSEQ assesses the frequency of sleep disturbance in 4 categories: 1) trouble falling asleep, 2) waking up several times during the night, 3) having trouble staying asleep (including waking up far too early), and 4) waking up after the usual amount of sleep feeling tired and worn out. Patients report the numbers of days they experience each of these problems in the past month on a 6 point Likert Scale ranging from 0 = “no days” to 5 = “22-30 days.”	JSEQ score	Sum of 4-item score (each on a 6-point Likert scale, 0 = no days and 5 = 22-30 days). Range: 0 to 20, higher scores indicating greater sleep disturbance (Deodhar et al. 2010)	Missing if >20% items (ie any of the 4) are missing
		JSEQ score change from baseline	Change from baseline calculated as: observed JSEQ – baseline JSEQ	Missing if baseline or observed value is missing
Quick Inventory of Depressive Symptomatology-self report 16 items	See Section 6.12.6 for description of QIDS-SR16	9 Domains	See Section 6.12.6 for description of each domain	See Section 6.12.6
		Change from baseline in each domain	Calculated as: observed domain score – baseline domain score	Missing if baseline or observed value is missing
		16 individual items	Range: 0 to 3.	Missing if the item is missing.
		Change from baseline in	Calculated as: observed individual item	Missing if baseline or item

Measure	Description	Variable	Derivation / Comment	Imputation Approach if with Missing Components
		each individual item	score – baseline individual item score	is missing
		QIDS-SR16 total score	See Section 6.12.6 for description of QIDS-SR16 total score	See Section 6.12.6
		Change from baseline in QIDS-SR16 total score	Calculated as: observed total score – baseline total score	Missing if baseline or observed value is missing
		Proportion of patients with at least a 50% decrease in QIDS-SR16 total score	% reduction from baseline calculated as: $100 \times \frac{\textit{Baseline} - \textit{Observed score}}{\textit{Baseline}}$ If the value of % reduction from baseline is ≥ 50 , patients had at least a 50% decrease in QIDS-SR16 total score.	Missing if baseline or observed score is missing

Abbreviations: ASAS = Assessment of Spondyloarthritis International Society; MCS = mental component summary; NRS = numeric rating scale; PCS = physical component summary.

Table RHBV.6.7. Description of Health Outcomes and Quality-of-Life Analyses

Measure	Variable	Analysis Method (Sections 6.1 and 6.3)	Population (Section 6.1.5)	Comparison/Time Point	Analysis Type
36 item Short Form Health Survey (SF-36)	PCS change from baseline – Major Secondary	MMRM	ITT Population	IXE80Q2W & IXE80Q4W vs. placebo at Week 16	Major secondary analysis is MMRM analysis for ITT Population comparing IXE80Q2W & IXE80Q4W vs. placebo at Week 16 (Section 6.10.2).
		MMRM	ITT Population	IXE80Q2W & IXE80Q4W vs. placebo at all other postbaseline visits in Period 2	Health Outcomes/QOL analyses (Section 6.10.6).
		ANCOVA with mBOCF/LOCF	ITT Population	IXE80Q2W & IXE80Q4W vs. placebo at Week 16 and all other postbaseline visits in Period 2	Health Outcomes/QOL analyses (Section 6.10.6).
		Descriptive statistics of change from baseline	Extended Treatment Period Population	No treatment group comparisons during Period 3	Health Outcomes/QOL analyses (Section 6.10.6).
		Descriptive statistics of change from baseline	ITT Population Who are Initially Randomized to Ixekizumab	No treatment group comparisons during Combined Periods 2 and 3	Health Outcomes/QOL analyses (Section 6.10.6).
	MCS, domain scores, change from baseline	MMRM	ITT Population	IXE80Q2W & IXE80Q4W vs. placebo at Week 16 and all other postbaseline visits in Period 2	Health Outcomes/QOL analyses (Section 6.10.6).
		ANCOVA with mBOCF	ITT Population	IXE80Q2W & IXE80Q4W vs. placebo at Week 16 and all other postbaseline visits in Period 2	Health Outcomes/QOL analyses (Section 6.10.6).
		Descriptive statistics of change from baseline	Extended Treatment Period Population	No treatment group comparisons during Period 3	Health Outcomes/QOL analyses (Section 6.10.6).

Measure	Variable	Analysis Method (Sections 6.1 and 6.3)	Population (Section 6.1.5)	Comparison/Time Point	Analysis Type
ASAS Health Index (ASAS-HI)	ASAS-HI change from baseline - Major Secondary	MMRM	ITT Population	IXE80Q2W & IXE80Q4W vs. placebo at Week 16	Major secondary analysis is MMRM analysis for ITT Population comparing IXE80Q2W & IXE80Q4W vs. placebo at Week 16 (Section 6.10.2).
		MMRM	ITT Population	IXE80Q2W & IXE80Q4W vs. placebo at all other postbaseline visits in Period 2	Health Outcomes/QOL analyses (Section 6.10.6).
		ANCOVA with mBOCF/LOCF	ITT Population	IXE80Q2W & IXE80Q4W vs. placebo at Week 16 and all other postbaseline visits in Period 2	Health Outcomes/QOL analyses (Section 6.10.6).
		Descriptive statistics of change from baseline	Extended Treatment Period Population	No treatment group comparisons during Period 3	Health Outcomes/QOL analyses (Section 6.10.6).
		Descriptive statistics of change from baseline	ITT Population Who are Initially Randomized to Ixekizumab	No treatment group comparisons during Combined Periods 2 and 3	Health Outcomes/QOL analyses (Section 6.10.6).
Fatigue Severity Numeric Rating Scale	Fatigue Severity change from baseline	MMRM	ITT Population	IXE80Q2W & IXE80Q4W vs. placebo at Week 16 and all other postbaseline visits in Period 2	Health Outcomes/QOL analyses (Section 6.10.6).
		ANCOVA with mBOCF	ITT Population	IXE80Q2W & IXE80Q4W vs. placebo at Week 16 and all other postbaseline visits in Period 2	Health Outcomes/QOL analyses (Section 6.10.6).
		Descriptive statistics	Extended Treatment Period Population	No treatment group comparisons during Period 3	Health Outcomes/QOL analyses (Section 6.10.6).

Measure	Variable	Analysis Method (Sections 6.1 and 6.3)	Population (Section 6.1.5)	Comparison/Time Point	Analysis Type
Work Productivity and Activity Impairment Questionnaire—Spondyloarthritis	Change from baseline in: 
 percentage of absenteeism percentage of presenteeism overall work impairment score percentage of impairment 	ANCOVA with mBOCF	ITT Population	IXE80Q2W & IXE80Q4W vs. placebo at Week 16 in Period 2	Health Outcomes/QOL analyses (Section 6.10.6).
		Descriptive statistics of change from baseline	Extended Treatment Period Population	No treatment group comparisons during Period 3	Health Outcomes/QOL analyses (Section 6.10.6).
JSEQ	JSEQ score change from baseline	MMRM	ITT Population	IXE80Q2W & IXE80Q4W vs. placebo at Week 16 and all other postbaseline visits in Period 2	Health Outcomes/QOL analyses (Section 6.10.6).
		ANCOVA with mBOCF	ITT Population	IXE80Q2W & IXE80Q4W vs. placebo at Week 16 and all other postbaseline visits in Period 2	Health Outcomes/QOL analyses (Section 6.10.6).
		Descriptive statistics of change from baseline	Extended Treatment Period Population	No treatment group comparisons during Period 3	Health Outcomes/QOL analyses (Section 6.10.6).
Quick Inventory of Depressive Symptomatology -self report 16 items	Change from baseline in the 9 QIDS-SR16 domains and 16 individual item score	ANCOVA with mBOCF	ITT Population ITT population with at least moderate depression at baseline (QIDS-SR 16 total score ≥ 11)	IXE80Q2W & IXE80Q4W vs. placebo at Week 16	Health Outcomes/QOL analyses (Section 6.10.6).
	Change from baseline in QIDS-SR16 total score	Descriptive statistics	Extended Treatment Period Population; Extension Period population with	No treatment group comparisons during Period 3	Health Outcomes/QOL analyses (Section 6.10.6).

Measure	Variable	Analysis Method (Sections 6.1 and 6.3)	Population (Section 6.1.5)	Comparison/Time Point	Analysis Type
			at least moderate depression at baseline (QIDS-SR16 total score ≥ 11)		
	Proportion of patients with at least a 50% decrease in QIDS-SR16 total score	Logistic regression with NRI; Fisher's exact test with NRI	ITT population for patients with at least moderate depression at baseline (QIDS-SR16 total score ≥ 11)	IXE80Q2W & IXE80Q4W vs. placebo at Week 16	Health Outcomes/QOL analyses (Section 6.10.6).
		Descriptive statistics with NRI	Extension Period Population with at least moderate depression at baseline (QIDS-SR16 total score ≥ 11)	No treatment group comparisons during Period 3	Health Outcomes/QOL analyses (Section 6.10.6).

Abbreviations: ANCOVA = analysis of covariance; ASAS = Assessment of Spondyloarthritis International Society; IXE80Q2W = ixekizumab 80 mg every 2 weeks; IXE80Q4W = ixekizumab 80 mg every 4 weeks; ITT = intent-to-treat; JSEQ = Jenkins Sleep Evaluation Questionnaire; mBOCF = modified baseline observation carried forward; MCS = mental component summary; MMRM = mixed-effects model of repeated measures; NRI = nonresponder imputation; PCS = physical component summary; QOL = quality of life.

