### **8.1.2.17. Work Productivity and Activity Impairment Questionnaire— Spondyloarthritis**

The WPAI-SpA consists of 6 questions to determine employment status, hours missed from work because of SpA, hours missed from work for other reasons, hours actually worked, the degree to which SpA affected work productivity while at work, and the degree to which SpA affected activities outside of work. The WPAI-SpA has been validated in the rad-axSpA patient population (Reilly et al. 2010). Four scores are derived: percentage of absenteeism, percentage of presenteeism (reduced productivity while at work), an overall work impairment score that combines absenteeism and presenteeism, and percentage of impairment in activities performed outside of work. Greater scores indicate greater impairment (Reilly Associates [WWW]).

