
Other secondary objectives are:
 
 • To compare both ixekizumab regimens (80 mg Q2W or 80 mg Q4W) to placebo during the 16-week placebo controlled period (Period 2) 	
 • Proportion of patients who achieve ASAS20, ASAS40, ASAS5/6, and partial remission by ASAS criteria • Change from baseline in the individual components of the ASAS criteria • Change from baseline in BASDAI • Proportion of patients reaching BASDAI50 • Change from baseline in ASDAS • Proportion of patients who experience clinically-important improvement (change of ASDAS from baseline ≥ 1.1), major improvement (change of ASDAS from baseline ≥ 2.0), inactive disease (ASDAS score < 1.3) and ASDAS < 2.1 • Change from baseline in the measure of high sensitivity C-reactive protein (CRP) • Change from baseline in BASFI • Change from baseline in mobility 
 ○ Bath Ankylosing Spondylitis Metrology Index (BASMI) (linear) and individual components ○ Chest expansion ○ Change from baseline in occiput to wall distance • Change from baseline in MRI of the SIJ (Spondyloarthritis Research Consortium of Canada Score [SPARCC]) • Change from baseline in SPARCC SIJ Structural Score (SSS) • Change from baseline in MRI of the spine (Ankylosing Spondylitis Spinal Magnetic Resonance Imaging activity–Berlin Score [ASSpiMRI-Berlin]) • Change from baseline in Maastricht Ankylosing Spondylitis Enthesitis Score (MASES) • Change from baseline in SPARCC Enthesitis Score • Incidence and severity of peripheral arthritis by tender (TJC) and swollen joint count scores (SJC) of 46/44 joints. • Incidence rate of anterior uveitis or uveitis flares • Change from baseline in the following health outcomes measures: Fatigue NRS score, ASAS-HI score, Jenkins Sleep Evaluation Questionnaire (JSEQ), Work Productivity Activity Impairment—Spondyloarthritis (WPAI-SpA) scores, SF-36 (both PCS and mental component scores [MCS]) and Quick Inventory of Depressive Symptomatology—Self Report 16 items (QIDS-SR16) score.

Secondary objectives continued	

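### The WPAI-SpA overall work impairment score is set to missing when Q5 is blank, even for a patient absent the whole week because of SpA, whose score the SAP's own formula fixes at 100%

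*SAP*

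**What the plan says.** SAP Table RHBV.6.6 derives four WPAI-SpA scores. Three matter here.

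- **Absenteeism** is Q2/(Q2+Q4) as a percentage. Its missing rule is "if Q2 or Q4 is missing, then missing".
- **Presenteeism** is Q5/10 as a percentage. Its missing rule is "if Q5 is missing, then missing".
- **Overall work impairment**, labelled as the percentage of "overall work impairment due to problem", is "Q2/(Q2+ Q4) + [(1-Q2/(Q2+Q4))*(Q5/10)])*100" (one opening bracket precedes this run in the table). Its missing rule is "if any of Q2, Q4, or Q5 is missing, then missing". There is no exception for a patient who worked no hours.

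The SAP describes the Q5 item as "the degree to which spondyloarthritis affected work productivity while at work", and Protocol Section 8.1.2.17 describes it in the same way. Higher scores are worse. The change from baseline is missing if either the baseline or the later score is missing.

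SAP Section 4 lists "Work Productivity Activity Impairment—Spondyloarthritis (WPAI-SpA) scores" among the other secondary endpoints. Table RHBV.6.7 compares each ixekizumab regimen with placebo at Week 16 by ANCOVA with mBOCF in the ITT population. In the Schedule of Activities (Protocol Appendix 2), WPAI-SpA is collected in Period 2 at Weeks 0 and 16 and not at screening. It is also collected at the early termination visit and at Week 52.

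**The concern.** An employed patient who was off work all week because of SpA did no work in that week, so there was no productivity at work to rate. If Q5 is left blank for that reason, the rule treats the patient as having given incomplete data. Yet Q2 and Q4 alone settle the score, and it is the worst value on the scale.

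Whether a score is lost then depends on the outcome itself. A patient fully absent at Week 16 drops out of the Week 16 comparison. A patient fully absent at baseline who returns to work has no change score, although that may be one of the largest improvements in the trial. Both patients keep an absenteeism score of 100% at the visit concerned. The combined score and one of its two components would therefore rest on different patients, selected by severity.

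**Working it through.** **Inputs.** The formula, the missing rules and the change-from-baseline rule come from SAP Table RHBV.6.6. The mBOCF rule comes from SAP Section 6.3.2, and the visit schedule from Protocol Appendix 2. The plan states no figure for this score that could be reproduced.

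**1. The formula when no hours were worked.** Let A = Q2/(Q2+Q4). The score is 100 × [A + (1 − A) × Q5/10]. With Q4 = 0 and Q2 > 0, A = Q2/Q2 = 1, the weight on Q5 is 1 − A = 0, and the score is 100 × 1 = 100%.

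| Q2 | Q4 | Q5 | Overall score | Absenteeism |
|---|---|---|---|---|
| 1, 8, 20 or 40 | 0 | every integer 0 to 10 | 100.0 in all 44 cases | 100.0 |
| 30 | 10 | 0 | 75.0 | 75.0 |
| 30 | 10 | 5 | 87.5 | 75.0 |
| 30 | 10 | 10 | 100.0 | 75.0 |
| 0 | 0 | any | 0/0, undefined | 0/0, undefined |

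The rows with 30 hours missed and 10 worked show that Q5 is needed once any hours were worked. The present rule is sound there. The last row is a second gap: the table gives no convention for a week with no hours worked and none missed because of SpA.

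**2. What the rule does when Q5 is blank.** With Q2 = 40, Q4 = 0 and Q5 blank, the formula needs nothing further and gives 100%, but the rule returns missing. A patient going from 100% at baseline to 30% at Week 16 has a true change of −70, which is recorded as missing.

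**3. Whether another rule restores the value.**
- mBOCF carries a value forward for patients who stop study drug. It has no provision for a patient on treatment with a blank score at Week 16. In Period 2 such a patient has no earlier postbaseline WPAI-SpA score to carry.
- The early termination visit supplies a score only for patients who discontinue, and that score is subject to the same missing rule.
- A missing baseline score has no fallback, because WPAI-SpA is not collected at screening. The loss extends to the Week 52 change as well.

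**4. Size.** Let f be the share of scored patients who were fully absent and m the mean score of the others. Restoring the deleted scores moves an arm's mean by [(1 − f) × m + f × 100] − m = f × (100 − m). The documents give neither f nor m, so the range below is assumed.

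| m | f = 2% | f = 5% | f = 10% |
|---|---|---|---|
| 30 | 1.4 | 3.5 | 7.0 |
| 40 | 1.2 | 3.0 | 6.0 |
| 50 | 1.0 | 2.5 | 5.0 |

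The shift in the difference between arms is the difference of two such terms. It is zero if f and m are the same in both arms.

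**The case against.** **Q5 may not be blank.** Neither document reproduces the questionnaire, and neither says how the ePRO tablet (Protocol Section 10.2.1) handles Q5 when no hours were worked. If any value is recorded, the present rule already gives 100% and nothing is lost. This stands. A blank Q5 is a reasonable inference from the wording of the item, not a documented fact, so the point is conditional. The proposed rule is harmless in either case.

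**The instrument's scoring instructions are not in the documents.** They may address this situation, and the point does not claim a departure from them. It claims only that the SAP's missing rule discards a value that the SAP's formula determines.

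**No bias has been shown.** A reader might infer that the rule hides a treatment benefit of known size. Suppose, purely as an assumption, 48 employed patients per arm, with 4 on placebo and 1 on ixekizumab fully absent at Week 16 and everyone else at 35%. The means are (44 × 35 + 4 × 100)/48 = 40.42 and (47 × 35 + 1 × 100)/48 = 36.35, a difference of 4.06 points, against 0 under the rule. The documents support none of these inputs. Setting both remaining groups to 35% puts the whole effect in the deleted patients. The example also uses raw Week 16 means, whereas the plan uses ANCOVA on change. With an assumed SD of 20 to 30, the standard error of the difference would be SD × √(2/48) = 4.1 to 6.1. The example shows a mechanism and nothing more.

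**Randomisation balances absence at baseline.** This is largely right. Exclusion on a baseline value is balanced between arms in expectation, so its main effect is to narrow the population and remove patients with room to improve. Loss at Week 16 comes after randomisation and depends on the outcome, so it has no such protection.

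**The information survives elsewhere.** The patients remain in the absenteeism and activity impairment scores. That limits the harm but does not repair the combined score.

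**Conclusion.** The rule gives a wrong result in one identifiable case: Q2>0, Q4=0 and Q5 blank. There it deletes a score that the SAP's own formula fixes at exactly 100%, and no other rule in either document puts it back for a patient still on treatment. That conclusion is algebraic. It needs only the premise that Q5 is blank for some such patients, which is likely but not stated.

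How often this happens, and the size and direction of any effect on the ixekizumab versus placebo difference, cannot be computed from the documents. The range of 1.0 to 7.0 points for an arm mean rests on assumed values of f and m.

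The consequence is limited to one score of one instrument among the other secondary outcomes, outside the multiplicity procedure in SAP Section 6.5. A reader should not infer any effect on ASAS40 or on the major secondary endpoints. WPAI-SpA is not among them. This is a modest correction, worth making because it costs so little.

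**What to change.** In SAP Table RHBV.6.6, replace the missing rule for the overall work impairment score with:

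- if Q4=0 and Q2>0, the score is 100% regardless of Q5;
- if Q2=Q4=0, the score is missing;
- otherwise, the score is missing if any of Q2, Q4 or Q5 is missing.

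Leave the presenteeism rule unchanged, since with no hours worked there is nothing for it to measure. Absenteeism has the same denominator, so it is worth stating the Q2=Q4=0 convention there too.

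The sponsor can confirm from the ePRO specification whether Q5 can be blank when Q4=0, and should check the new wording against the instrument's scoring instructions. Reporting the number of patients with Q2>0, Q4=0 and Q5 blank, by arm and visit, would show whether the point mattered in practice.

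The cost is one table entry and one or two programming conditions. No new data are needed.
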